## 10.2. Pharmacokinetic Concentration Data

For the creation of individual PK profiles reporting means and medians using the linear scale, all PK concentrations below the quantification limit (BQL) will be set to zero except when the sampling time of an individual BQL value falls immediately between the sampling times of two quantifiable values, in which case it will be set to missing.

When creating geometric summary statistics or log-linear plots, values that are BQL will be set to missing. No other procedures for replacing or imputing missing data are planned for any summarizations. If a subject has data points missing, that subject will be excluded from the analysis for that day and/or time point. If 24 hour samples that were taken post the next day’s dose, those samples will be excluded in the summary statistics for the 24 hour time point.

## 10.3. Baseline Definition

Baseline is the last available assessment prior to the time of first dose unless otherwise specified.

The study qualifying attack rate will be used as baseline for the attack rate endpoint and is defined as follows:

Subject Reported Qualifying attack rate:

$$\frac{\text{Total Number of Qualifying attacks reported} * 7}{\text{Duration of Qualifying reporting period in days}}$$

Duration of qualifying attack reporting period is calculated as number of days as the last date of the period – the first date of the reporting period +1.

Adjusted Qualifying attack rate:

$$\frac{\text{Total Number of Adjusted Qualifying attacks reported} * 7}{\text{Duration of Qualifying reporting period in days}}$$

Duration of qualifying attack reporting period is calculated as number of days as the last date of the period – the first date of the reporting period +1

For subject reported historical attacks on consecutive days, these attacks will be counted as a single attack in the calculation of the adjusted qualifying attack.

#### **10.4. Change from Baseline**

Change from baseline is calculated as:

$$\text{change from baseline value} = \text{'visit' value} - \text{baseline value}$$

Percent change from baseline is calculated as

$$\% \text{ change from baseline value} = (\text{'visit' value} - \text{baseline value}) * 100 / \text{Baseline Value}$$

The change and % change from baseline will be indicated as missing, if either the baseline or post-dose value is missing. Baseline is the last assessment prior to the date of first dose.

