#### **8.3.2.1. Discontinuation Due to QT Prolongation**

Any subject will be discontinued from further study drug dosing if the following QTcF criteria are met:

- The subject has a QTcF > 500 msec  
or
- The subject has a QTcF increase of more than 60 msec (confirmed by repeat ECG) from the mean QTcF value obtained from triplicate ECGs obtained predose on Day 1.

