#### **9.4. Study Drug (Investigational Medicinal Product) Administration and Treatment Compliance**

Subjects will take all study drug doses at home with the exception of study drug that will be administered under Investigator (or designee) supervision during scheduled on-treatment clinic visits on Days 1, 14 and 15 (and Day 28 if applicable). Subjects will be instructed to take 3 capsules (Parts 1 and 2) or 2 capsules (Parts 3 and 4) of study drug orally QD in the morning for 28 days. Subjects will be instructed to take study drug with food, or within 30 minutes after consuming food. On Days 1, 14 and 29, subjects should fast for 8 hours prior to their blood draw for laboratory testing.

The first dose of study drug will be administered in the clinic on Day 1. For study Days 14 and 15, subjects should be instructed to refrain from taking study drug prior to their visit to obtain a trough and/or serial blood draws at steady state.

On in-clinic dosing days (Days 1, 14 and 15), subjects will be required to consume food within 30 minutes prior to dosing (but after any blood draws for safety laboratory testing); the requirements for type and amount of food is to be provided to the subject (e.g., number of

servings of protein, carbohydrate, and/or fat) will be communicated in a separate document. On all other days, subjects should take the study drug in the morning with food (or within 30 minutes after consuming food). It is recommended that the study drug be administered with food in order to help minimize gastrointestinal effects. If gastrointestinal-related symptoms are noted as an AE, the site should query the subject and record whether the drug is being taken as instructed (i.e., with food).

Subjects will be instructed to maintain approximately the same daily dosing interval between study drug doses. If a subject forgets to take the study drug at the correct time, the dose may be taken later in the day; however, no more than 1 dose of BCX7353 should be taken on any calendar day. The subject should resume the standing regular dosing schedule on the next day.

Subjects will be instructed to record in their diary the time of day study drug was taken, and the number of capsules of study drug taken.

Subjects will be instructed to bring all drug kits (including both unused and used kit bottles) and diaries with them for each study visit. Accountability and adherence will be reviewed at each clinic visit.

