#### **11.1.10. Other Laboratory Assessments**

Troponin I, Troponin T, NGAL and CK-MB will be measured in this study at the following time points: Day 1, Day 14, Day 29, and follow-up/early termination. C3 level will be taken at Baseline only unless required for AE assessment (see Section 12.2.1).

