#### **11.1.14. Pharmacodynamics**

On Day 1 and Day 14 a plasma sample for plasma kallikrein analysis will be drawn prior to dosing and, on Day 14, at 1, 2, 3, 4, 5, 6, 8, and 24 hours postdose. The Sponsor may waive the participation in any or all serial PD sampling on a case by case basis. A sample for plasma kallikrein analysis will also be drawn on Day 29.

A plasma sample for possible exploratory analysis used to elucidate PD properties of BCX7353 will be drawn on Day 1, Day 14, and Day 29.

Instructions for collection, processing, storage and shipment of samples will be provided in a separate document.

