## **11.2. Subject-Completed Assessments**

### **11.2.1. Quality of Life Questionnaires**

To assess quality of life, the AE-QoL and DASS questionnaires will be administered once at Baseline, Day 14 (DASS only) and at Day 29.

For all subject-completed forms, clinic staff should ensure the subject reads the instructions and completes the questionnaires in full prior to filing in the source documentation.

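### SAP 10.4 cuts baseline off at the date of first dose, in conflict with SAP 10.3 and with the protocol's Day 1 pre-dose baseline

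*SAP*

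**What the plan says.** SAP 10.3, the section headed as the baseline definition, states: "Baseline is the last available assessment prior to the time of first dose unless otherwise specified". It then makes the qualifying attack rate the baseline for the attack-rate endpoint.

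SAP 10.4 gives the formulas for change and percent change, adds that "The change and % change from baseline will be indicated as missing, if either the baseline or post-dose value is missing", and closes with "Baseline is the last assessment prior to the date of first dose".

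Protocol 9.4 fixes the date concerned: "The first dose of study drug will be administered in the clinic on Day 1".

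Several variables are first measured at that same visit:
- Protocol 11.2.1: "the AE-QoL and DASS questionnaires will be administered once at Baseline, Day 14 (DASS only) and at Day 29".
- Protocol 11.1.10: "Troponin I, Troponin T, NGAL and CK-MB will be measured in this study at the following time points: Day 1, Day 14, Day 29", and again at follow-up.
- Protocol 11.1.14: "On Day 1 and Day 14 a plasma sample for plasma kallikrein analysis will be drawn prior to dosing".

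**The concern.** Two adjacent SAP sections give different cut-offs. A value obtained on the morning of Day 1 before dosing precedes the time of first dose but does not precede its date. It is therefore a baseline under 10.3 and is excluded under 10.4.

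The proviso at the end of the 10.3 sentence does not settle the matter. It allows exceptions stated elsewhere, and 10.4, which governs change scores, can be read as one.

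Two programmers could each follow the SAP and produce different tables. At stake are the quality-of-life, pharmacodynamic and cardiac-marker changes, which could be lost, and the laboratory, vital-sign and ECG changes, which could be computed from the wrong reference.

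**Working it through.** The plan gives no figure to reproduce and no arithmetic is needed. The check takes each baseline-dependent variable, finds its pre-treatment collection times (protocol Table 3 and SAP Table 1 with footnotes; protocol 10.3.1, 10.3.2 and section 11), and applies each rule.

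**Step 1. Dates.** First dose is on Day 1. Under 10.4 only Day -1 or earlier qualifies. Screening runs from Day -21 to Day -1. Protocol 10.3.2 lets a listed set of Day 1 procedures move to Day -1 for logistical reasons.

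**Step 2. Apply both rules.**

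| Variable | Pre-treatment collection | Baseline under 10.3 | Baseline under 10.4, literal |
|---|---|---|---|
| Plasma kallikrein | Day 1 pre-dose; not on the Day -1 list | Day 1 | None in any subject on schedule |
| AE-QoL, DASS, cleaved HK, troponin I/T, NGAL, CK-MB | Day 1 pre-dose; Day -1 permitted | Day 1 (or Day -1) | None unless taken on Day -1 |
| C1 INH function | Day 1 in all; screening only without historical results; Day -1 permitted | Day 1 (or Day -1) | Screening or Day -1 sample if there is one, otherwise none |
| Chemistry, hematology, coagulation, urinalysis, vital signs, weight | Screening and Day 1; Day -1 permitted | Day 1 (or Day -1) | Screening, up to 21 days earlier (or Day -1) |
| ECG | Single at screening; triplicate on Day 1; Day -1 permitted | Mean of 3 readings | 1 screening reading (or Day -1 triplicate) |
| Attack rate | Qualifying period | Qualifying attack rate | Unaffected; defined separately in 10.3 |

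One detail within chemistry: protocol Table 4 limits the lipid panel to Baseline and Day 29, so lipids belong with the second row.

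**Step 3. Follow the missing baselines.** SAP 10.4 sets the change to missing when baseline is missing. The analyses that rest on these values are:
- the AE-QoL and DASS models on change from baseline (SAP 12.1.4.1 and 12.1.4.2);
- kallikrein inhibition, expressed relative to each subject's own baseline activity (SAP 14.1);
- the cleaved HK and C1 INH change models, which also use baseline as a covariate (SAP 14.1).

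SAP 6.6.2 requires a baseline value for membership of the cleaved HK and C1 INH populations, so those populations would shrink too.

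**Step 4. Follow the shifted baselines.** SAP 12.5.2 calls a laboratory abnormality treatment-emergent if it is at least one grade above baseline. Take a hypothetical subject with ALT at Grade 0 at screening, Grade 1 on Day 1 pre-dose and Grade 1 on Day 14. Under 10.3 the Day 14 value is not treatment-emergent; under 10.4 it is. The reference matters here because protocol 5.3.3.1 already names elevated baseline ALT and AST as a possible confounder, and SAP section 16 plans tables of liver-test fold change from baseline. In the same way, the QTcF change categories in SAP 12.7 (above 30 up to 60 msec, and above 60 msec) would be counted from one screening ECG.

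**Step 5. Apply the correction.** With time in place of date, every Day 1 pre-dose value and every permitted Day -1 value qualifies. None of the changes in the table is then missing by rule.

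**The case against.** The strongest reply is that nobody would read 10.4 this way. Both schedules label the Day 1 column as baseline, the protocol visit bears that title, and the questionnaires are described as given at baseline. SAP 12.1.4.1 and 12.1.4.2 list baseline as an analysis visit. Section 10.3 carries the definition, while 10.4 only restates it loosely and does not claim to override. Empty AE-QoL, DASS or kallikrein tables would be noticed at once. Protocol 5.3.3.2 already reports kallikrein inhibition against baseline samples from Parts 1 and 2, although the documents do not show which SAP version governed those outputs.

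Most of this stands. A reader might infer that the SAP discards every Day 1 baseline and that the quality-of-life and pharmacodynamic results will be empty. The documents do not support that, because the loss arises only if 10.4 is coded as written.

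Three narrower inferences also fail:
- Renal and muscle markers as a class would not go missing. Creatinine, creatinine clearance, creatine kinase and the urine microalbumin ratio are in panels also taken at screening, so they would shift rather than vanish.
- The QTcF discontinuation criterion in protocol 8.3.2.1 would not change. It is measured "from the mean QTcF value obtained from triplicate ECGs obtained predose on Day 1", whatever the SAP says.
- The ECG triplicate is not left undefined. Protocol 11.1.4 averages the three readings, and SAP 10.5 averages repeated measurements at one time point.

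The claim that the error would reveal itself does not fully stand. It holds for empty tables but not for the fallback to screening values, which yields complete and plausible output.

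**Conclusion.** SAP 10.4 is wrong as written and should be corrected. It contradicts SAP 10.3 and the protocol's Day 1 pre-dose baseline, and the text alone establishes this.

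The consequence is conditional on literal programming. In that case the loss is complete for kallikrein inhibition among subjects on schedule. For the Day 1 questionnaires, cleaved HK, troponin, NGAL and CK-MB it is complete apart from subjects assessed on Day -1, and for C1 INH it is partial. The documents do not give the number of subjects with Day -1 or screening samples, so the loss for these variables cannot be quantified further. The quieter effect is a reference up to 21 days too early for routine laboratory tests, vital signs, weight and ECG.

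The primary attack-rate endpoint is untouched, and the surrounding text makes clear that 10.3 is intended.

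**What to change.** Delete the last sentence of SAP 10.4, or change date to time and refer to 10.3 as the single definition. Two optional clarifications would help: that ECG baseline is the mean of the Day 1 pre-dose triplicate, as in protocol 11.1.4, and how a Day 1 assessment with no recorded clock time is treated.

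The cost is a line or two of SAP wording, with no new data and no change to the protocol. SAP 11.3 already allows computational algorithms to be refined.

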#### **10.5. Multiple Measurements at One Time Point**

Where multiple measurements are recorded for a particular time point, the mean of the measurements will be calculated and used in any derivation of summary statistics. All available data will be listed.

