#### 11.1.4. 12-lead Electrocardiograms

A standard bedside 12-lead ECG machine that calculates heart rate and measures the PR, QRS, QT, RR, and QTc (QTcF) intervals will be utilized. Prior to obtaining an ECG, subjects must rest quietly in a supine position for at least 10 minutes.

Qualified site personnel should review the ECGs and automated findings in real-time for gross abnormalities and interval measurements of concern (absolute readings and for postdose ECGs, change from baseline). For all ECGs, the clinical interpretation of the ECG should be recorded directly on a hard copy of the ECGs. Copies of the ECGs may be requested by the Sponsor.

Baseline (predose) ECGs will be obtained in triplicate (i.e., 3 separate readings) at 1- to 5-minute intervals, with baseline values calculated from an average of the 3 readings. All other ECGs will be single assessments.

An ECG should be repeated for a change from baseline in QTcF > 60 msec or a QTcF interval > 500 msec.

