### **12.2. Toxicity Management**

The Investigator (or qualified designee) will grade clinically significant events and laboratory abnormalities (if considered AEs) according to that detailed in Section 12.1.3. Grade 3 and 4 clinically significant laboratory abnormalities should be confirmed by repeat testing and before any contemplated study drug/IMP discontinuation, unless such a delay is not consistent with good medical practice.

In the event that 2 subjects experience similar Grade 3 or 4 treatment-emergent laboratory abnormalities or AEs that are suspected to be drug related as determined by the Investigator and not otherwise physiologically explained, a DMC meeting will be immediately convened by the Sponsor. Based on the data presented, a decision will be made as to whether to halt the study, to continue dosing, or to continue dosing with provisions introduced into the protocol via substantial amendment.

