### **9.2. Reporting Conventions**

Data analyses will be performed by, or under the direct supervision of, BioCryst Pharmaceuticals, Inc., Durham, NC.

Listings will be sorted by treatment, subject, and planned assessment time point. Summaries will be presented by treatment, study day and planned assessment time point. Unless stated otherwise, descriptive summaries will include n, mean, standard deviation, coefficient of variation (CV) or Q1, Q3 and 95% CI, median, minimum, and maximum for continuous variables, and n and percent for categorical variables. In addition, for log normally distributed parameters, the geometric mean with associated 95% CI, between-subject CVs (CVb), and SD of the logs based on the geometric mean, will be included.

The between-subject %CV of the log transformed variable will be calculated as

$\%CV_b = 100 * \sqrt{(e^{SD^2} - 1)}$ , with SD of the log-transformed data.

For summary tables, the following reporting convention will be used unless otherwise stated:

Frequencies (safety)	Counts (n)	None
	Percentages (%)	1 decimal place
Summary statistic (safety, number of attacks, reported QOL and PK)	n	None
	Mean	i + 1 decimal place
	Median	i decimal places
	SD	i + 1 decimal place
	Min	i decimal places
	Max	i decimal places
	CV%	none
	Geometric n	None
	Geometric Mean	i + 1 decimal place
	Geometric CV%	none
Statistical Analyses, reporting of derived efficacy and QOL endpoints	Derived efficacy end points (%)	1 decimal place
	Other derived efficacy endpoints	2 decimal places
	p-values	if <0.001: presented as <0.001 ; >0.999, presented as >0.999
		if ≥0.001 and ≤0.999: presented to 3 decimal places

i refers to the number of decimal places reported in the source workbook or other appropriate source data for the original data

Deviations from the analyses in the SAP will be identified in the final Clinical Study Report.

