## **12.7. Electrocardiograms**

The ECG data and change from baseline values will be listed and summarized by treatment, visit and planned time. The number and proportion of subjects with QTcF >450, >480 or >500 msec; or changes of >30 -≤60 msec, or >60 msec will be summarized by treatment over time.

Clinically significant abnormal ECG findings will also be summarized.

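### SAP 10.5 averages a QTcF reading above 500 msec with the repeat it triggers, and SAP 12.7 has no worst-value rule, so a subject stopped on that reading can drop out of the >500 row

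*SAP*

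**What the plan says.** **Averaging.** SAP 10.5 covers any time point with more than one measurement: "the mean of the measurements will be calculated and used in any derivation of summary statistics". It makes no exception for repeats or for safety outliers. It adds that all data will be listed. SAP 10.7 places descriptive summaries on nominal times.

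**Which ECGs are repeated.** Under Protocol 11.1.4 the predose baseline ECG is a triplicate and every other ECG is a single reading. The same section gives the trigger for a second one: "An ECG should be repeated for a change from baseline in QTcF > 60 msec or a QTcF interval > 500 msec".

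**Stopping.** Protocol 8.3.2.1 has two criteria. The first reads "The subject has a QTcF > 500 msec" and mentions no confirmation. The second, an increase of more than 60 msec, has to be confirmed by a repeat ECG.

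**Tabulation.** SAP 12.7 promises "The number and proportion of subjects with QTcF >450, >480 or >500 msec", with categories for change as well, by treatment over time. Table 14.3.6.3 presents these by visit. Neither place says which reading counts when a visit has two. SAP 9.2 includes "n and percent for categorical variables" in its description of the descriptive summaries.

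**The concern.** Averaging is sensible for planned replicates, because the number of readings does not depend on their values. After baseline the position is different. A second ECG at a visit normally exists because the first crossed a limit. A rule that replaces the pair by its mean therefore acts almost only on extreme values and usually pulls them down. A table meant to count outliers would then omit some of them.

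The point has some weight for this drug. Protocol 5.2.2 reports hERG inhibition in vitro (IC50 0.29 µM), and 5.4.4.2 says ECGs will be done until the human effects are better understood. The dose arms are small. Part 2 (14 subjects, 1:3:3) and Part 3 (20 subjects, 1:3:3:3) give 6 + 6 = 12 subjects at 250 mg, and Part 3 gives 6 at 62.5 mg. One missed subject is 1/12 = 8% or 1/6 = 17% of such an arm.

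**Working it through.** The plan states no figure to reproduce. The check applies SAP 10.5 to a pair of readings and then asks how often the result matters.

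**Step 1: the arithmetic of the rule.** The tabulated value is (first + repeat) / 2. A first reading of 500 + x is brought to 500 or below when the repeat is 500 − x or lower.

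| First | Repeat | Mean | Row by highest reading | Row by mean |
|---|---|---|---|---|
| 505 | 490 | 497.5 | >500 | >480 |
| 510 | 488 | 499.0 | >500 | >480 |
| 515 | 484 | 499.5 | >500 | >480 |
| 510 | 495 | 502.5 | >500 | >500 |

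In the first three rows the first reading alone meets the 8.3.2.1 criterion, yet the subject is not counted above 500. The fourth row shows that this does not always happen.

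**Step 2: how often.** Let T be the true QTcF, and let X1 and X2 be independent normal readings with mean T and standard deviation s. Neither T nor s is in the documents. I take s from 5 to 15 msec and T at 495, 500 and 505. The quantity is

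P(mean ≤ 500 | X1 > 500) = P(X1 > 500 and X1 + X2 ≤ 1000) / P(X1 > 500).

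At T = 500 it does not depend on s. By symmetry the numerator is 1/8 and the denominator 1/2, giving 1/4.

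| True QTcF | s = 5 | s = 8 | s = 15 |
|---|---|---|---|
| 505 | 3% | 8% | 14% |
| 500 | 25% | 25% | 25% |
| 495 | 67% | 51% | 38% |

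These probabilities are conditional on a first reading above 500. They do not say how often such a reading will occur.

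**Step 3: the 60 msec criterion.** A subject stopped on it has a first change above 60 and a confirming change above 60. The mean of two numbers above 60 is above 60, so that subject stays in the row. A pair such as +64 and +54 averages +59 and leaves the row, but the repeat did not confirm the rise, so the subject was not stopped on that criterion.

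**Step 4: laboratory grades.** Protocol 12.2 says "Grade 3 and 4 clinically significant laboratory abnormalities should be confirmed by repeat testing", so repeats arise there too. However, SAP 12.5 brings in all laboratory assessments after first dose, and SAP 12.5.2 uses the highest post-baseline grade in the shift table. Those specific rules largely settle the matter. What is missing is a statement that they override 10.5.

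**The case against.** The best reply is that 10.5 may not reach the QTcF counts at all. It speaks of summary statistics, and the reporting table in SAP 9.2 lists safety frequencies separately from summary statistics. On that reading a count of subjects above 500 is a frequency, and the individual readings decide it. This stands as a possible reading. It is not the more natural one, because the text of 9.2 puts counts and percents among the descriptive summaries and 10.5 applies to any derivation. Two programmers could reasonably differ.

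Further points also stand:

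- The averaging needs the repeat to share the nominal time point with the first ECG. The SAP has no rule for repeat or unscheduled ECGs, so one logged separately might not be averaged.
- Protocol 11.1.4 says an ECG should be repeated, which is softer than a requirement.
- Where the true value is at or below 500, averaging arguably removes a false positive. The figures for 495 and 500 should be read in that light; only the 3-14% at 505 concerns a true exceedance.
- The event may be rare. Screening excludes QTcF above 470 msec, the one treatment-emergent value above 450 msec that Protocol 5.3.1 reports was 455 msec, and Protocol 5.3.3.1 reports no clinically significant QTcF finding in Parts 1 and 2.
- Nothing is hidden. Listing 16.2.9.2 covers the ECGs, and SAP 11.1 tabulates discontinuations of study drug with reasons.

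A reader might infer more: that subjects stopped on the 60 msec criterion are lost too, or that the Grade 3/4 laboratory endpoint is biased downward. Steps 3 and 4 show why the documents do not support either inference.

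**Conclusion.** The point holds as a gap in the analysis rule for QTcF categories. On the natural reading of SAP 10.5 with 10.7 and 12.7, and if the repeat is recorded at the same nominal visit, a subject removed from drug on a single QTcF above 500 msec can be tabulated at 500 or below. The table would then disagree with the ECG listing and the discontinuation record.

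Given a first reading above 500, the chance of this is about 3-14% at a true value of 505, 25% at 500 and 38-67% at 495. This assumes independent, normally distributed readings with SD 5 to 15 msec, which the documents do not give. The number of subjects affected may well be zero or one, but in arms of 6 to 12 a single subject changes the table. For laboratory grades the issue is only one of stated precedence. It should be settled before database lock.

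**What to change.** 1. In SAP 10.5, limit averaging to planned replicates (the Day 1 triplicate ECG) and to continuous by-visit means.
2. In SAP 12.7 and the notes to Table 14.3.6.3, state that QTcF categories use the highest individual post-dose reading per subject, per visit and overall, with repeat and unscheduled ECGs included. Add a flag for readings confirmed by a repeat.
3. In SAP 12.5.2, add a cross-reference saying that the maximum post-baseline grade is taken over individual results and takes precedence over 10.5.

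The cost is a few sentences of SAP text and a small programming change. The downside is that outlier counts may be slightly higher because unconfirmed readings are counted; the flag lets a reader separate them. Nothing here touches the clinical stopping criteria in Protocol 8.3.2.1.
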